20.2 Appendix B. Coaching Intervention – No Internet Access to DSI Tool51

LIST OF ABBREVIATIONS

ACS	American Cancer Society
AE	adverse event
AS	Active Surveillance
AUA	American Urological Association
BX	Biopsy
CAPRA	Cancer of the Prostate Risk Assessment score
CaPSURE	Cancer of the Prostate Strategic Urologic Research Endeavor
CFR	Code of Federal Regulations
CP	Choice Predisposition
CPS	Control Preferences Scale
CRF	case report form
CROM	Clinician-reported outcome measure
CRC	Clinical Research Coordinator
D&L	Diet and lifestyle
DMC	Data Monitoring Committee
DNA	Deoxyribonucleic acid
DoD-TIA	Department of Defense Transformative Impact Award
DSE	Decision Self-efficacy
DSI	Decision Support Intervention
DSMB	Data Safety Monitoring Board
DQI	Decision Quality Instrument
ECOG	Eastern Cooperative Oncology Group (ECOG) performance status
EPIC	Expanded Prostate Index Composite-26 items
FDA	Food and Drug Administration
FFPE	Formalin Fixed Paraffin Embedded
GCP	Good Clinical Practice
HIPAA	Health Insurance Portability and Accountability Act of 1996
ICF	informed consent form
ICH	International Conference on Harmonisation

IEC	Independent Ethics Committee
IRB	Institutional Review Board
MaxPC	Memorial Anxiety Scale for Prostate Cancer (MAX-PC)
MRI	Magnetic Resonance Imaging
PCa	Prostate Cancer
PCa SCOPED	Prostate Cancer SCOPED Form (S ituation, C hoice, O bjectives, P eople, E valuation, and D ecision)
PI	Principal Investigator
PIVOT	Prostate Intervention Versus Observation Trial
PSA	Prostate Specific Antigen
PROM	Patient-reported Outcome Measures
QL	Question List – Summary Form
QOL	Quality of Life
RNA	Ribonucleic acid
SAE	serious adverse experience
SSCa	Service Satisfaction with Cancer Care
SF-12	Short Form-12 (4-week recall)
TIBI-CaP	Total Illness Burden Index – Prostate Cancer
TRUS	Transrectal Ultrasound
US/UG	Up-staging / Up-grading

PROTOCOL SYNOPSIS

TITLE	DoD-TIA RCT PCa Decision Tool
SPONSOR	University of California San Francisco; Dept. of Urology
FUNDING ORGANIZATION	Department of Defense (DoD) U.S. Dept. of the Army Military Medical Research and Development
NUMBER OF SITES	4
RATIONALE	
Current clinical-pathologic descriptions of prostate cancer (e.g. grade, stage, PSA) can be used to estimate a patient's risk of harboring more aggressive disease and the risk of recurrence post-therapy. However, there are limited data on how well patients understand this information and how this affects their management decisions. Decision support tools have been proposed to help men with prostate cancer through their decision process, yet most are not tailored to a patient's unique biology or preferences.¹¹
 
Our study evaluates the first decision support intervention that uses service learning (student) coaches as a low-cost workforce to administer a decision aid with personalized risk estimates based on patient tumor features. In a single-arm pilot study at UCSF, we found this intervention was feasible and acceptable, and associated with increased patient knowledge (IRIS #14-13332). We now propose to evaluate this decision support intervention in a multi-site clinical trial.

STUDY DESIGN	This is a site-randomized, cluster-crossover clinical trial of a decision support intervention (DSI) vs. usual care, among men with low prognostic risk prostate cancer, to assess differences in informed decision making (i.e., knowledge), anxiety, and decision quality and self-efficacy.
PRIMARY OBJECTIVE	To assess the impact of the DSI on knowledge (i.e., informed decision-making) regarding risks associated with different management strategies for prostate cancer, given one is diagnosed with low-risk prostate cancer.
SECONDARY OBJECTIVES	1). To assess the impact of the DSI on anxiety, decision quality and self-efficacy. 2). After the DSI or usual care, to compare choice of prostate cancer management / treatment selected.
NUMBER OF SUBJECTS	160 subjects enrolled, allowing for attrition (12) and non-response (12), leaving ~136 fully evaluable subjects.
SUBJECT SELECTION CRITERIA	
Inclusion Criteria: A patient diagnosed with prostate cancer who meets the following criteria:
 
 1. PSA \leq 15 ng/ml

	
 1. Clinical stage cT1/2,N0,M0 2. Biopsy Gleason grade 2-6 OR (or 3+4 AND <=33% cores are positive for adenocarcinoma); 
 a. A minimum of 10 diagnostic cores taken by a systematic directed approach. Sampling may be obtained by target TRUS or MRI imaging. 3. No treatment yet 
 a. No previous radiation or simultaneous use of androgen deprivation b. Prior use of 5-alpha reductase inhibitor is allowed if they have been stopped for 6 or more months and biopsy performed when patient was not taking the drug. 4. English language proficient and ability to sign an ICF 5. Considered candidates for active surveillance at their institution by the treating urologist. 
Exclusion Criteria: Participants who have received any therapy for prostate cancer or who do not read/speak English or whose managing urologist does NOT deem them as a candidate for active surveillance.

TEST PRODUCT, DOSE, AND ROUTE OF ADMINISTRATION
	
Participants assigned to the intervention will receive Decision Support in the form of a decision aid+health coaching. The decision aid (delivered by internet and as a PDF document) provides participants with a report on options and outcomes as described in the literature; along with more tailored risk information. The tailored risk information will include their estimated risk of harboring more aggressive prostate cancer based on their clinical/pathologic features (i.e., “My Clinical Risk”). The DSI was developed and piloted at UCSF according to the International Patient Decision Aid Standards (see http://ipdas.ohri.ca/) (IRS# 14-13332), and incorporates tailored risk models developed and validated at UCSF and community sites [1]. The tailored models estimate a patient’s risk of having more aggressive prostate cancer if, theoretically, one was to remove their prostate gland at that time (i.e., undergo surgery as active treatment) and have the entire gland reviewed (i.e., risk of up-staging or up-grading (US/UG)).

CONTROL PRODUCT, DOSE AND ROUTE OF ADMINISTRATION
	
Participants assigned to the control arm will receive usual care, including whatever information materials are provided to them by their urologist. (We will assess what materials they reviewed by surveying patients.)

DURATION OF SUBJECT PARTICIPATION AND DURATION OF STUDY	Subjects will be in an active study phase for approximately 4-6 weeks, depending on their scheduling with their local urologist. Within those six weeks, we will approach them about the study; if interested/consented, they will be asked to complete baseline surveys online (paper will be available if preferred); access the decision aid; and talk to the health coach; complete pre-visit surveys; meet with their urologist; and complete follow-up surveys. Once the participant has met with his urologist and made a management decision, he is done with the active intervention phase of the study, and will roll-over into an observational cohort component only of the study. In this phase, we will ask participants to complete surveys on their prostate cancer status and quality of life annually and allow us to access their medical chart to abstract data on their health and prostate cancer status.
CONCOMITANT MEDICATIONS	
Allowed: Participants may take any medications unrelated to their prostate cancer during the study. After their visit with their local urologist when they make a management decision, participants may follow any medical regimen for their prostate cancer.
 
Prohibited: We will not enroll participants who have already received treatment for their prostate cancer.

EFFICACY EVALUATIONS	
PRIMARY ENDPOINT	
 • Knowledge regarding the risks and benefits associated with different management choices for men with localized/early stage prostate cancer.
SECONDARY ENDPOINTS	
 • Anxiety, decision self-efficacy, health-related quality of life. • Choice of prostate cancer management / treatment selection.
OTHER EVALUATIONS	Optional: In the future, we may consider banking saliva and FFPE tumor tissue from already performed biopsies for future research studies. Biospecimen donation will be optional.
SAFETY EVALUATIONS	There are not planned safety evaluations. The active phase of this behavioral intervention is brief, ~4-6 weeks. Participants will not be receiving any active treatment for their cancer during this phase. The main risks may be anxiety or confusion regarding the risks and benefits associated with their current diagnosis and decision ahead, and risk of loss to privacy by participating in a research study.
PLANNED INTERIM ANALYSES	As a behavioral intervention trial testing knowledge as the primary outcome, there an interim analysis is not planned.

STATISTICS Primary Analysis Plan	We will use univariate statistical tests (e.g., chi-square, t-test) and multivariate regression to assess the difference in the probability of the primary outcome between subjects randomized to the intervention and control arms for each site.
Rationale for Number of Subjects	Standard power calculations for chi-square tests to compare two proportions along with adjustments for potential correlation of responses within sites, missing data and attrition show that tests based on a sample of 136 subjects would have power to detect an alternative where the probability of the primary response increases from 0.5 in the control sites to 0.75 in the intervention sites. We will enroll 160 subjects to allow for attrition and survey non-response.

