15.3 Analysis of Primary Endpoint

The primary statistical analysis will compare the probability of correctly responding to the two knowledge survey questions between subjects randomized to the intervention and control sites using logistic regression. The primary predictor of the logistic model will be the binary, site-specific intervention indicator. We will also include site, time and intervention group by time interaction terms. Since randomization by site may not balance, all relevant sociodemographic and clinical characteristics of the subjects may be included in the models; we will also include other factors that are not balanced between the groups. We will assess balance by comparing means of continuous characteristics using two sample t-tests and by comparing categorical characteristics using chi-square tests.

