15.6 Sample Size and Randomization

We will base sample size calculations on the comparison of the probability of correctly responding to the two survey questions between subjects at the intervention versus control sites with a design effect correction to accommodate the potential correlation of responses within sites [44]. That is, we will inflate the sample sizes resulting from standard sample calculations for the comparison of two proportions by the design effect, $1 + (n-1)*\rho$, where n is the sample size per site and ρ is the intraclass correlation coefficient of the primary binary response[45]. We are interested in detecting an alternative where the probability of the primary response increases from 0.5 in the control sites to 0.75 in the intervention sites. Standard power calculations for chi-square tests to compare two proportions [45] show that tests based on a total sample size of 116 would have power 0.8 to detect the alternative of interest. Since our study design involves 8 clusters (four sites measured in two time periods), our initial design would include 15 subjects measured in each site at each time. Preliminary data indicate that the intraclass correlation coefficient of the primary response is quite low within sites; the estimated intraclass correlation coefficient was less than 0.01. This estimate produces a design effect of 1.14 and we inflate the required number of subjects per site and time to 17 for a total sample size of 136.

Randomization: At baseline, this study will randomize two sites to the intervention and two sites to serve as controls. There are six possible assignments of two intervention and control sites in our study and we will generate a uniform (0,1) random number to select one of them.

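### The synopsis lists several tests for the primary outcome and names none as decisive, which conflicts with the single logistic regression designated in section 15.3

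*Combined protocol and SAP*

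**What the plan says.** Three places in the combined protocol and SAP bear on the primary test.

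- **Protocol Synopsis, Statistics, Primary Analysis Plan.** The row begins "We will use univariate statistical tests (e.g., chi-square, t-test) and multivariate regression" and applies these methods to the primary outcome, compared "between subjects randomized to the intervention and control arms for each site". The tests are given as examples and none is ranked above the others.
- **Section 15.3.** "The primary statistical analysis will compare the probability of correctly responding to the two knowledge survey questions", by logistic regression. On the effect of interest the section is explicit: "The primary predictor of the logistic model will be the binary, site-specific intervention indicator". For the rest of the model it adds: "We will also include site, time and intervention group by time interaction terms". On covariates, "all relevant sociodemographic and clinical characteristics of the subjects may be included in the models", and factors found unbalanced are added. T-tests and chi-square tests appear here only as the means of judging that balance.
- **Section 15.6.** The sample size rests on "Standard power calculations for chi-square tests to compare two proportions", inflated by a design effect to 136 men in total. The synopsis row on the number of subjects uses the same pooled 136.

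No alpha level or sidedness is stated. Section 15 says that a SAP, to be written before the final data are analysed, will hold any modifications.

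**The concern.** The synopsis and section 15.3 give chi-square tests and t-tests different jobs: tests of the primary outcome in one, balance checks in the other. They also appear to differ on whether the comparison is made within sites or across them. These analyses would give different p-values, and nothing in the document says which text prevails. If the choice is still open when results are known, the most favourable result can be reported as primary and the nominal error rate no longer holds.

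The phrase about sites adds a second question. Every site contributes men to both arms after crossover (section 8.1), so a separate test within each site is possible and is a natural literal reading. The trial was not sized for that.

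**Working it through.** **Inputs.** Section 15.6 gives response probabilities of 0.50 (control) and 0.75 (intervention), power 0.8, total 116 before inflation, eight site-periods, an intraclass correlation below 0.01, a design effect of 1.14, and 17 men per site-period after inflation. Section 8.1 gives 20 enrolled per site-period. Two-sided 5% is assumed.

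**Reproducing the plan's figures.** Per arm, n = [1.960·√(2·0.625·0.375) + 0.842·√(0.25 + 0.1875)]² / 0.25² = (1.342 + 0.557)² / 0.0625 ≈ 57.7, so 58 per arm and 116 in total, as stated. One-sided 5% would give 92, and two-sided with continuity correction 132, so two-sided 5% without correction is the variant that fits. Then 116/8 = 14.5, rounded to 15; the design effect is 1 + 14 × 0.01 = 1.14; 15 × 1.14 = 17.1, taken as 17; and 17 × 8 = 136. The trial's size is that of one pooled comparison.

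**Power under each reading of the synopsis.** Power = Φ[(0.25·√n − 1.342)/0.661], with n per arm.

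| Reading | n per arm | Power |
|---|---|---|
| Separate test in each site, evaluable men | 17 | Φ(−0.470) = 0.319 |
| Separate test in each site, all enrolled | 20 | Φ(−0.338) = 0.368 |
| Pooled, no clustering | 68 | Φ(1.088) = 0.862 |
| Pooled, design effect 1.14 | 68/1.14 = 59.6 | Φ(0.890) = 0.813 |

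Exact enumeration of the uncorrected chi-square test gives 33.2% at 17 versus 17 and 37.5% at 20 versus 20; Fisher's exact test gives 21.3% and 26.9%. Recomputing the design effect at 17 per cluster (1.16) moves the pooled figure only to 0.807. Power of 80% within every site would need 58 × 2 × 4 = 464 men.

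**Can section 15.3 be copied into the synopsis as it stands?** Take time as the two study periods. Let b = 1 for a site that starts in usual care, t = 1 in period 2, and x = 1 under intervention. In this crossover x = 1 − b − t + 2bt, and x·t = bt. Hence x·t = (x − 1 + b + t)/2. With fixed site effects, b is a sum of site indicators, so the interaction is an exact linear combination of terms already in the model. The design matrix has rank 6 for 7 columns. The same holds if the interaction is meant as starting group by period, because that product is also a linear combination of b, t and x. With the interaction removed, a simulation of the pooled model with site and period (3,000 runs, 17 per site-period, no site, period or cluster effects) gave about 87% power, in line with the 86% above.

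**The case against.** The strongest reply is that the protocol does name a primary analysis. Section 15.3 uses that term for the logistic regression and identifies its primary predictor, so the synopsis is only a loose summary. This stands. A reader might infer that the trial has no single primary test; the documents do not support that. Nor is section 15.6 a rival primary analysis. It is a sizing formula, and sizing on two proportions before analysing by adjusted regression is common practice.

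A reader might also infer that the synopsis analysis is badly underpowered. That depends on one reading of an ambiguous phrase. It can equally mean the arm assigned to each site, and the next synopsis row bases power on the pooled 136. On that reading power is about 81%. Likewise, the familywise error of 1 − 0.95⁴ = 18.5% for four site tests would require independent tests at 5% each and a rule that any one significant site counts as success. No such rule appears anywhere.

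Finally, the promised SAP and the statistician's blinding to the sites' assignment during analysis (section 8.2) lessen the risk of a results-driven choice. They do not remove it. The SAP is deferred and may modify the plan, and two-sided p-values from different tests can be compared without knowing the arm labels.

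**Conclusion.** The contradiction between the synopsis and section 15.3 is real and should be removed before analysis. On the pooled reading, the synopsis is adequately powered but still leaves several candidate tests for the primary outcome. On the literal within-site reading, power is about 32% per site at the planned evaluable numbers (37% at full enrolment) against about 81% for the pooled comparison. Only the pooled analysis agrees with the trial's own sample size.

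Section 15.3 is the better text but cannot simply be copied. Its interaction term is not estimable with fixed site effects, and its covariates are discretionary.

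The power figures rest on an assumed two-sided 5% level and, for the pooled case, an intraclass correlation at its stated upper bound of 0.01. The estimability result assumes fixed site effects and time coded as two periods.

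**What to change.** State the same primary analysis in the synopsis row and in section 15.3, and carry it into the SAP:

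- one pooled logistic model for answering both knowledge items correctly, with intervention, site and period;
- no intervention-by-time term;
- any covariates listed in advance, with none added on the strength of balance tests;
- the intervention effect tested once, at a stated two-sided 5% level.

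Label chi-square tests, t-tests and per-site proportions for the primary outcome as descriptive. The cost is wording in the synopsis and section 15.3. Sample size and conduct do not change.

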1 BACKGROUND

A critical public health need exists for **improved prognostic tools to distinguish aggressive from indolent prostate cancer** at diagnosis, and for **better support systems to guide patients in decision-making regarding management options**. Our proposal addresses both needs, and is poised to improve management of low-risk prostate cancer in the United States (U.S.) in the near term.

1.1 Overview of Non-Clinical Studies

Patients generally are at risk for both under-treatment and over-treatment relative to their personal priorities and the best available medical evidence [2-4]. This is certainly true in the case of low-risk prostate cancer patients, who are often over-treated with surgery or radiation relative to what they say they would have preferred if fully informed about all the options and outcomes, including the risks and benefits of active surveillance.

Decision support interventions tailored to specific clinical crossroads have increased patient self-efficacy, knowledge, question-asking, and satisfaction; and decreased decisional conflict, regret, anxiety, and distress [2, 5-17]. Such informed and involved patients tend to pursue less invasive treatment options than they might otherwise settle upon under usual care [18, 19].

However, in the area of prostate cancer, these decision support interventions have not provided personalized risk estimates to patients. The need for personalized risk estimates arises from the potential for an initially low-risk prostate cancer to be reclassified over time if it is not treated with surgery or radiation. Many patients and physicians avert that risk by erring on the side of active treatment (surgery or radiation) rather than active surveillance.

To reduce the risk of over-treatment, our team has developed individual risk prediction models that we have now integrated into our decision support intervention (DSI).

Decision support interventions must be delivered to patients in an effective and efficient manner. Our team has refined a comprehensive DSI, which prompts patients to review risk and other educational materials, as well list questions in writing for their physicians [7]. We have also refined a service learning workforce to deliver the intervention remotely, by internet and telephone, in a way that does not require clinics to modify their practices, and that leverages unpaid student interns receiving academic credit as part of their academic training [7].

Delivering such decision support should increase patient knowledge and question-asking, and these proximal outcomes should increase the proportion of men making informed decisions regarding their selection of active surveillance, surgery, or radiation for low-risk prostate cancer. This study will evaluate whether our intervention is feasible and effective in delivering individually tailored decision support to men prior to their first urology visit upon diagnosis with low-risk prostate cancer; and whether a higher proportion of men make informed decisions with less anxiety or decisional regret.

1.2 Overview of Clinical Studies

Not applicable

2 STUDY RATIONALE

Age-adjusted mortality rates have fallen nearly 40% since the start of the prostate specific antigen (PSA) screening era, and are at their lowest level in the past 80 years [20]. Prostate cancer remains the second leading cause of cancer mortality among men in the U.S.[20], but a wide array of novel diagnostic and therapeutic interventions promise to drive mortality rates down further.

The Prostate Intervention Versus Observation Trial (PIVOT) reported an early survival benefit for men diagnosed with high-risk disease (e.g., prostate cancer of high grade, stage, and/or PSA) treated with surgery rather than observation—but no benefit for men with low-risk disease [21, 22]. Moreover, all treatments entail risk of long-term quality of life (QOL) impacts (e.g. erectile dysfunction, incontinence) [23], and many men—often those opting for newer, technology-intensive treatments—ultimately express regret regarding their treatment decisions and low satisfaction with their clinical or QOL outcomes [24].

A growing consensus deems current rates of over-treatment of low-risk prostate cancer unacceptable, as the morbidity associated with avoidable interventions accounts for much of the suffering associated with prostate cancer in the U.S. [25]. One solution is to screen more selectively, to reserve treatment for men with aggressive cancer, and to guide those with indolent, lower-risk disease to active surveillance (AS)—i.e., careful monitoring with serial assessments and curative treatment at any sign of progression [26, 27]. Multiple factors underlie over-treatment of low-risk disease; key among them is the concern that a biopsy may not fully reflect tumor aggressiveness. The rate of biopsy under-sampling—i.e., a biopsy indicating low-risk characteristics for a tumor that ultimately proves to be higher grade or stage—is estimated at 20-30% [28].

Decision support tools have been proposed to help men with prostate cancer through their decision process, yet most are not tailored to a patient’s unique biology or preferences [29].

Our study evaluates the first decision support intervention that uses service learning (student) coaches as a low-cost workforce to administer a decision aid with personalized risk estimates based on patient biology. In a single-arm pilot study at UCSF, we found this intervention was feasible and acceptable, and associated with increased patient knowledge.

